11.6 Conflict of interest

The independence of the study's conduct and results from any actual or perceived external influences is critical. Therefore, any current conflict of interest of any person playing a role in the design, conduct, analysis, publication, or any other aspect of this study will be declared. Furthermore, those with a perceived conflict of interest will be asked to manage it in a manner appropriate to their participation in the study.

11.7 Access to information

The final study database will be the property of Laboratorios Sophia, SA de CV, and access to it will be restricted. The PI will not have access to it except with prior written authorization from the sponsor.

Any information obtained that is relevant to the safety of the subjects participating in the study must be immediately shared with the research center, so that the study subjects can be notified.

11.8 Auxiliary and post-study care

Once the study is completed and adverse events are closed in accordance with section 8, the sponsor will not extend care to the research subject.

12. Biosecurity aspects

NO BIOSECURITY IMPLICATIONS

This protocol, entitled: "Phase I clinical study to evaluate the safety and tolerability of PRO-185 ophthalmic solution applied in clinically healthy subjects," and number: SOPH185-0521/I, HAS NO BIOSAFETY IMPLICATIONS, since no infectious biological material will be used; pathogenic strains of bacteria or parasites; viruses of any type; radioactive material of any type; genetically modified animals and/or cells and/or plants; toxic, hazardous, or explosive substances; or any other material that puts the health or physical integrity of the research center staff or research subjects at risk, or affects the environment. It is also declared that no cell, tissue, or organ transplant procedures, or cell therapy, will be carried out in this project, nor will laboratory, farm, or wildlife animals be used.

13. Publication Policy

13.1 Final report

Once the statistical analysis is completed, the final report will be written with the results obtained, by the Medical Management Department Team of Laboratorios Sophia, SA de CV. This report will be prepared following the recommendations of the *ICH E3 Step 4 Guide*.

13.2 Communication of results

Regardless of the results of the study, Laboratorios Sophia, SA de CV, is committed to communicating the final study report to the principal investigators and COFEPRIS. These results will also be shared with the research committee and the IEC. The PI will be responsible for communicating the results to the research subjects.

Laboratorios Sophia, SA de CV will retain at all times the rights to the publication and dissemination of the information contained herein.

13.3 Publication of results

Laboratorios Sophia, SA de CV, acting as the sponsor of the study, assumes full responsibility for its role and retains exclusive ownership rights to the study results, which it may use as it sees fit.

The PI agrees not to publish or communicate data collected from the study, unless prior written agreement is obtained from Laboratorios Sophia, SA de CV. Any manuscript derived from the data obtained with this protocol must be reviewed by the sponsor before any attempt to submit it for publication in any journal or scientific conference.

However, if the sponsor is in the process of filing a patent application on the results of the study, the sponsor may delay publication or communication of the results of the study until the date of registration or when it deems appropriate.

The assignment of authors for publications derived from this research will be the sole responsibility of the sponsor. Researchers invited to participate as authors must express their authorization. All researchers who will participate as authors may review the article prior to submission and are free to make comments and suggestions within the first 15 calendar days of receipt.

14. Financing and insurance

14.1 Compensation to study participants

Subjects participating in the study may receive financial compensation for their participation. Compensation may vary depending on the activities required during each visit.

16.1 Efron scale for conjunctival hyperemia

16.2 SICCA Ocular Staining Grading (modified from Whitcher et al, 2010)

Score by staining pattern																					
Lissamine green (conjunctiva only) 
  
 Grade	Score	
   
 0	0-9	
 
 1	10-32	
 
 2	33-100	
 
 3	>100	
  
 Additional points for fluorescein staining only: 
 +1 if there are patches of confluent staining +1 if there is staining in the pupillary area +1 if there are filaments 	Grade	Score	0	0-9	1	10-32	2	33-100	3	>100	Fluorescein (cornea only) 
  
 Grade	Score	
   
 0	0	
 
 1	1-5	
 
 2	6-30	
 
 3	>30	
  
	Grade	Score	0	0	1	1-5	2	6-30	3	>30
Grade	Score																				
0	0-9																				
1	10-32																				
2	33-100																				
3	>100																				
Grade	Score																				
0	0																				
1	1-5																				
2	6-30																				
3	>30																				

16.3 Review of articles for sample size calculation

Reference	Summary	Subjects	Treatment

Reference	Summary	Subjects	Treatment
	
redness remained significant from baseline for 8 hours after a single instillation for both vasoconstrictors and for 6 hours after multiple administrations of naphazoline.
 
The decrease in tetrahydrozoline's effectiveness after the 10-day study period may encourage its overuse. No vasoconstrictor produced rebound vasodilation after discontinuation.
		
The efficacy of oxymetazoline and naphazoline (0.01%) was evaluated in 20 patients with red eye. The decongestive effect of oxymetazoline 0.01% on days 3 and 7 was 66.66% and 80.55%, compared with 22.22% and 50% for naphazoline 0.01%. Oxymetazoline showed a significant improvement in conjunctival symptoms such as itching, foreign body sensation, tearing, and burning with naphazoline compared with oxymetazoline. No ocular toxicity or AEs were observed during the study.
	20	Naphazoline 0.01%
This review provides a current, clinically relevant summary of the mechanism of action, efficacy, and safety of available OCT decongestants for the reduction of ocular redness caused by minor irritations. Currently, the OCT products marketed in the US include tetrahydrozoline 0.05%, naphazoline 0.012% to 0.03% , and brimonidine 0.025%. All 3 agents are adrenergic receptor agonists but vary in their receptor-binding properties: tetrahydrozoline is a selective α1-adrenergic receptor agonist, naphazoline is a combination α1/α2 receptor agonist, and brimonidine is a selective α2 receptor agonist. These OCT decongestants produce vasoconstriction of conjunctival blood vessels, resulting in a rapid reduction of ocular redness. In general, reported ocular AEs are minimal, mild, and transient, with no significant systemic AEs. However , ocular decongestants with α1-adrenergic receptor agonist activity have been associated with loss of effectiveness after continued use (tachyphylaxis) and rebound redness upon discontinuation. In clinical studies,
	146	Naphazoline 0.012 to 0.03%

Reference	Summary	Subjects	Treatment
	brimonidine has not been associated with tachyphylaxis, and rebound redness has been rarely reported.

## 1. Abbreviations

AO	Both eyes
AVMC	Best corrected visual acuity
OF	Standard deviation
EA	Adverse event
eCRF	Electronic Case Report Form
FC	Heart rate
FCI	Informed Consent Form
FR	Respiratory rate
ICH	International Council for Harmonization of Technical Requirements of Pharmaceuticals for Human Use )
ITT	Intention-to-treat population
KS	Kolmogorov-Smirnov
bpm	Beats per minute
PAD	Diastolic blood pressure
PAE	Statistical analysis plan
PAS	Systolic blood pressure
PI	Investigational Product
PIO	Intraocular pressure
PP	Population by protocol
PRO-185 Naphazoline Hydrochloride 0.03%	
rpm	Breaths per minute
SDV	Source document verification
SEC	Self-evident correction
SW	Shapiro-Wilk
TF	Fluorescein staining
TVL	Lissamine green staining
X 	Chi square

## 2. Introduction

This document describes the statistical analysis plan (SAP) designed for the SOPH185 protocol. 0521/I (Phase I clinical study to evaluate the safety and tolerability of PRO-185 ophthalmic solution applied to clinically healthy subjects). This PAE is intended to complement the study protocol. Any deviation from this document will be described in the Final Clinical Study Report [1].

## 3. Study Design

This is a Phase I, controlled, non-comparative, open-label, single-center clinical study, see Figure 1.

### 3.1 Objectives

#### 3.1.1 Main objective

To evaluate the safety and tolerability of PRO-185 ophthalmic solution in ophthalmologically healthy subjects.

#### 3.1.2 Specific objectives

- To evaluate the safety of PRO-185 ophthalmic solution by the incidence of subjects who present an increase  $>5$  mmHg in intraocular pressure (IOP) after 20 minutes of its application compared to the initial value.
- To evaluate the safety of PRO-185 ophthalmic solution by the incidence of subjects presenting a heart rate change  $>15$  beats per minute (bpm) 20 minutes after application.
- To evaluate the safety of PRO-185 ophthalmic solution by the incidence of subjects presenting an increase in systolic blood pressure (SBP)  $>15$  mmHg or  $>10$  mmHg in diastolic blood pressure (DBP) after 20 minutes of its application.
- Evaluate tolerability by the incidence of grade 3 and 4 conjunctival hyperemia.
- Evaluate tolerability by the incidence of pharmacological mydriasis.
- Evaluate tolerability by the incidence of expected and unexpected adverse events (AEs). expected.

### 3.2 Study Hypothesis

#### 3.2.1 Null hypothesis (H0)

PRO-185 ophthalmic solution is not safe and tolerable for ophthalmic use because more than 10% of subjects experienced any of the following AEs: increased IOP (>5 mmHg), changes in HR (>15 bpm), increased systemic blood pressure (>15 mmHg SBP or >10 mmHg DBP), pharmacological mydriasis, or grade 3 and 4 conjunctival hyperemia.

$$H_0 = p - p_0 \leq \delta$$

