3.2 Hypothesis

H_0 = PRO-185 ophthalmic solution is safe and tolerable for ophthalmic use, as it occurred in 20% or less of subjects with any of the following adverse events: increased intraocular pressure (IOP >5 mmHg), heart rate variation (>15 bpm), increased systemic blood pressure [>15 mmHg systolic (SBP) or >10 mmHg diastolic (DBP)], pharmacological mydriasis, or grade 3 and 4 conjunctival hyperemia.

$$H_0: p - p_0 \leq \delta$$

H_1 = PRO-185 ophthalmic solution is not safe or tolerable for ophthalmic application because more than 20% of subjects experienced any of the following adverse events: increased IOP (>5 mmHg), heart rate variation (>15 bpm), increased systemic blood pressure [>15 mmHg systolic (SBP) or >10 mmHg diastolic (DBP)], pharmacological mydriasis, or grade 3 and 4 conjunctival hyperemia.

$$H_1: p - p_0 > \delta$$

Comparisons will be made between pre- and post-treatment measurements from visits 1 and 2, and between measurements from the baseline visit (before PT application) and measurements from the

final visit. Only one of the adverse event values described in the hypothesis need be abnormal with a frequency >20% between the comparisons (pre-treatment with post-treatment; or pre-PT baseline with values from the final visit) for the null hypothesis to be rejected.

4. Study design

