10.1.1 Calculation methodology

A search was performed on the open access search engines PubMed (pubmed.ncbi.nlm.nih.gov) and Web of Science (webofscience.com), finding until May 2021, 102 results in PubMed and 24 in Web of Science that matched the search keywords: “*Naphazoline Ophthalmic*”. The extraction of this search was generated and the integrated database was reviewed, to eliminate duplicate matches and filter those articles that were in accordance with the objective of the study. After reviewing the *abstracts* (available only in 89 articles), 7 articles were chosen for their complete review (full text), of these, 5 articles were selected to make the proposal for the sample size [47, 48, 49, 50], one of them is a review article [51], this was used only as a reference. See appendix 16.3.

The mean \pm standard deviation (SD) sample size used in the selected studies was 24.4 ± 21.24 subjects (range, 6–60). Considering a 20% incidence rate for AEs, these values were entered into an online tool [52] to estimate sample size and power, following specific equations for the calculation [53]. Finally, the calculated value was increased by 20% to account for potential losses.

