10.1.2 Size calculation

PRO-185 ophthalmic solution is expected to present in less than 20% of subjects any of the following AEs: increased IOP (>5 mmHg), heart rate changes (>15 bpm), increased systemic blood pressure (>15 mmHg in SBP or >10 mmHg in DBP), pharmacological mydriasis or grade 3 and 4 conjunctival hyperemia, 20 minutes after its application with respect to its initial value.

The sample size was calculated using the equation for a non-superiority proportion [53]. This equation is useful for non-inferiority/superiority tests, if we want to test whether a proportion (p) is not superior to a reference value, p_0 (20% in this case). The idea is that statistically significant differences between the proportion and the reference value cannot be of interest unless the difference is greater than a threshold δ (10% in this case). This type of calculation is useful in clinical studies where the value of δ is chosen based on clinical judgment and knowledge of the subject.

The hypothesis test is:

$$H_0: p - p_0 \leq \delta$$

$$H_1: p - p_0 > \delta$$

Equations

The calculation to estimate the sample size and power was performed using an online tool and following the equations [53]:

$$18 = p(1 - 0.2) \left(\frac{1.96 + z_{1-\beta}}{p - 0.2 - 0.1} \right)^2$$

$$1 - \beta = \Phi(z - 1.96) + \Phi(-z - 1.96), z = \frac{p - 0.2 - 0.1}{\sqrt{\frac{p(1 - 0.2)}{18}}}$$

Where:

n is the sample size (18)

p₀ is the reference value (0.20)

Φ is the function of the standard normal distribution

Φ⁻¹ is the function of the standard normal distribution

α is the Type I error (1.96)

β is the Type II error, which means that, 1-β (1-0.8) is the power

δ is the test margin (0.10)

According to the previous calculation, 18 subjects are estimated, increasing the calculation by 20% considering possible losses, 22 subjects are estimated to contribute OA to the study. This calculation is in accordance with the average number of subjects used in the clinical studies reviewed in the search performed in PubMed and Web of Science (24 subjects), where the incidence of adverse events was similar to that expected in this study.

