10.3.2 Safety and tolerability analysis

10.3.2.1 Analysis for primary variables

The analysis of safety and tolerability outcomes will be conducted in the safety population, defined as all subjects who received at least one dose of the investigational product (PRO-185), regardless of their adherence to the protocol (intention-to-treat, ITT, population).

Statistical analysis for the primary quantitative variables will be estimated using the Wilcoxon signed-rank test for a sample for the difference in measurements before and after treatment for visits 1 and 2, while the baseline visit (pre-PT) will be compared against the final visit, once the values have been adjusted with respect to their baseline within each individual.

For conjunctival hyperemia, the X^2 binomial test or Fisher's exact test will be used for expected values less than 5.

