#### 3.2.2 Alternative hypothesis (H1)

PRO-185 ophthalmic solution is safe and tolerable for ophthalmic use, as it did not present any of the following AEs in more than 10% of subjects: increased IOP (>5 mmHg), changes in HR (>15 bpm), increased systemic blood pressure (>15 mmHg in SBP or >10 mmHg in DBP), pharmacological mydriasis, or grade 3 and 4 conjunctival hyperemia.

$$H_1 = p - p_0 > \delta$$

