### 4.1 Calculation methodology

A search was carried out in the open access search engines PubMed (pubmed.ncbi.nlm.nih.gov) and Web of Science (webofscience.com), finding until May 2021, 102 results in PubMed and 24 in Web of Science that matched the keywords of

Search: "Naphazoline Ophthalmic". The extract was generated from this search, and the integrated database was reviewed to eliminate duplicate matches and filter out those articles that were consistent with the study objective. After reviewing the *abstracts* (available only in 89 articles), 7 articles were selected for full-text review. Of these, 5 articles were selected to make the sample size proposal.

[2, 3, 4, 5], one of them is a review article [6], this was used only as a reference (see [Annex 9.1](#)).

The mean  $\pm$  standard deviation (SD) sample size used in the selected studies was  $24.4 \pm 21.24$  subjects (range 6–60). Considering a 10% proportion in the incidence of AEs, these values were entered into an online tool [7] to estimate the sample size and power, following the specific equations for the calculation [8].

Finally, the calculated value was increased by 20% to account for possible losses.

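### The protocol and SAP state opposite null hypotheses at different limits (20% and 10%), neither matches its own symbols, and nothing says which document prevails

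*SAP*

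**What the plan says.** **Protocol, sections 1.1 and 3.2.** The null hypothesis is that "PRO-185 ophthalmic solution is safe and tolerable for ophthalmic use, as it occurred in 20% or less of subjects with any of the following" events: raised intraocular pressure, heart-rate variation, raised blood pressure, pharmacological mydriasis, or grade 3 and 4 hyperemia. The alternative is that the product is not safe, with more than 20% affected. The rejection rule is "Only one of the adverse event values described in the hypothesis need be abnormal with a frequency >20% between the comparisons". The comparisons are before against after treatment at visits 1 and 2, and baseline (before dilation) against the final visit.

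**SAP, sections 3.2.1 and 3.2.2.** The null hypothesis is that "PRO-185 ophthalmic solution is not safe and tolerable for ophthalmic use because more than 10% of subjects experienced any of the following AEs". The alternative is that the product is safe, "as it did not present any of the following AEs in more than 10% of subjects". The SAP has no counterpart to the protocol's rejection rule.

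**Symbols.** Both documents print H0: p − p0 ≤ δ and H1: p − p0 > δ. Protocol section 10.1.2 sets p0 at 20% and says a difference is not of interest "unless the difference is greater than a threshold δ (10% in this case"). SAP section 4.2 also gives δ = 10% but no value for p0.

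**Sample size.** Protocol section 10.1.1: "Considering a 20% incidence rate for AEs, these values were entered into an online tool". SAP section 4.1: "Considering a 10% proportion in the incidence of AEs, these values were entered into an online tool". Both arrive at 18 evaluable subjects; the planned number is 22.

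**Tests.** Protocol section 10.3.2.1 gives "For conjunctival hyperemia, the X^2 binomial test" or Fisher's exact test, and a one-sample Wilcoxon signed-rank test for the quantitative primary variables. SAP section 6.2.1 gives Kolmogorov-Smirnov, Mann-Whitney, Pearson or Fisher.

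**Status of the SAP.** Section 2 says it complements the protocol and that departures from it go in the final report. Section 7 records no changes.

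**The concern.** The hypothesis is the plan's own safe/not-safe verdict on its five primary variables. As written, the verdict is not defined:

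- The starting presumption is safety in one document and lack of safety in the other.
- Three limits are in play: 10% (SAP words), 20% (protocol words) and 30% (protocol symbols).
- In the SAP, the symbolic alternative means more events, while the worded alternative means safe.
- The named tests do not settle it. Wilcoxon tests on measured values do not test an incidence against a limit, and the binomial test for hyperemia has no stated null proportion.

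The same data could therefore be reported as safe under one document and not safe under the other, and the choice could be made after the data are seen. Reporting a departure from the SAP afterwards does not fix the rule beforehand.

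**Working it through.** **1. Limit implied by the protocol's symbols.** p0 + δ = 0.20 + 0.10 = 0.30, against 20% in its words.

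**2. The stated 18 (22).** Formula: n = variance × ((1.96 + 0.8416)/(p − p0 − δ))². The 1.96 is from protocol section 10.1.2; 0.8416 corresponds to 80% power. The protocol's printed equation enters no number for p.

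| Reading | Calculation | n |
|---|---|---|
| p = 0.10 (SAP 4.1), limit 0.30 (protocol 10.1.2), variance p(1 − p) | 0.09 × (2.8016/0.2)² = 17.66 | 18 |
| Same, with the protocol's printed variance p(1 − 0.2) | 0.08 × (2.8016/0.2)² = 15.70 | 16 |
| The protocol's 20% taken as the true rate, limit 0.30 | 0.16 × (2.8016/0.1)² = 125.6 | 126 |
| The SAP's 10% taken as both p and p0, limit 0.20 | 0.09 × (2.8016/0.1)² = 70.6 | 71 |

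Adding 20%: 18 × 1.2 = 21.6, so 22. The figure is reproduced, but only with p from one document and the limit from the other. That design shows that a true rate of 10% lies below 30%. This is opposite to the printed H1 and at neither worded limit.

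**3. Conflict zone when the limits are cut-offs on the observed percentage.** With 22 evaluable, the protocol passes up to 4 events (4/22 = 18.2%; 5/22 = 22.7%) and the SAP up to 2 (2/22 = 9.1%; 3/22 = 13.6%). They disagree at 3 and 4 events. With 18 evaluable they disagree at 2 and 3 (11.1%, 16.7%). Exact binomial probabilities of landing there:

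| True rate | 5% | 10% | 15% | 20% |
|---|---|---|---|---|
| One count, n = 22, P(3 ≤ X ≤ 4) | 9% | 32% | 44% | 39% |
| One count, n = 18, P(2 ≤ X ≤ 3) | 22% | 45% | 50% | 40% |
| Five components, n = 22, P(X ≤ 4)⁵ − P(X ≤ 2)⁵ | 37% | 63% | 27% | 5% |

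All rows cover one comparison only. The last row assumes independent components with equal rates, which the documents do not support; it shows only that the reading matters.

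**4. Chance that one count passes, n = 22.**

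| True rate | 10% | 20% | 30% |
|---|---|---|---|
| Protocol, ≤ 4 events | 94% | 54% | 16% |
| SAP, ≤ 2 events | 62% | 15% | 2% |

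**5. Precision in the disputed zone.** Exact 95% intervals: 3/22 gives 2.9–34.9%; 4/22 gives 5.2–40.3%. Both contain 10%, 20% and 30%.

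**6. The hypotheses read as tests.** Assume an exact one-sided 5% binomial test with 22 subjects; neither document specifies one. Under the SAP, even 0/22 gives P = 0.9²² = 0.098, so safety could never be shown; at least 29 event-free subjects would be needed (0.9²⁸ = 0.052, 0.9²⁹ = 0.047). Under the protocol's 20%, safety is rejected only from 9/22 (P = 0.020; 8/22 gives 0.056). The documents then disagree from 0 to 8 events.

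**The case against.** The conflict itself is not in dispute. The reservations concern what is built on it.

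- **The SAP contains no observed-percentage rule**, so the 3-or-4-event figures rest on one reading. This stands. Read as tests, the disagreement is wider (0 to 8 events), so the figures illustrate the problem and do not measure it for the whole study. The 94% pass probability is likewise for one count; under the five-independent-components assumption it is 0.938⁵ = 73%.
- **The protocol already favours a per-component rule and names the comparisons.** Largely true. These points are open mainly in the SAP, and the protocol's answer needs carrying across.
- **p = 0.10 is inferred, and other values also give 18.** True: about 0.62 with variance p(1 − p), or about 0.107 with the printed variance. No document states either rate. The protocol assigns its 20% to p0, so the 126 is one reading of an ambiguous sentence, as is the 71.
- **The SAP may simply be out of date.** Plausible: it keeps SPSS 19.0 and tests that protocol version 2.0 replaced. But nothing supplied says it is superseded, and the protocol's change history records no change of limit or direction. Replacing the SAP would also leave the protocol's own 20% against 30%.
- **Front pages were removed**, so the absence of a precedence rule can be judged only on the supplied text. That limit is accepted.

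**Conclusion.** The concern holds and must be fixed. The opposite nulls, the 20% and 10% limits, the SAP's symbols against its own words and the protocol's symbolic limit of 30% are all on the face of the operative text. They need no assumption.

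The size depends on the decision rule, which the documents do not settle. With limits on the observed percentage, 22 evaluable and one count at one comparison, the verdicts conflict with probability 9% to 44% at true rates of 5% to 20%; with 18 evaluable, 22% to 50%. With an exact one-sided 5% test, the SAP could not conclude safety on any data from 22 subjects. That no document prevails is judged on the supplied text.

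**What to change.** - State one hypothesis pair in both documents, with one direction, one limit justified by the sponsor, and symbols (with values for p0 and δ) that match the words.
- State in both whether the limit applies per component or to the composite, and at which comparisons.
- Say whether the verdict uses the observed percentage or a one-sample binomial test with a stated null proportion and one-sided alpha, for all five components.
- Update the SAP to protocol version 2.0, and say which document prevails.
- Restate every sample-size input (p, p0, δ, variance form, alpha, power), and give the power of the chosen rule at 18 and 22 subjects.
- Report each incidence with its exact 95% confidence interval.

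**Cost.** Text in protocol sections 1.1, 3.2, 10.1 and 10.3.2.1 and SAP sections 2, 3.2, 4, 6 and 7, a reworked sample-size paragraph, and committee approval of the amendment. Reconciling the wording needs no extra subjects or visits; some choices of tested limit would, as the 10% case shows.

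**Optional.** If the aim is to demonstrate safety, make an unacceptable rate the null and judge by the exact upper bound. Against 30% at one-sided 2.5%, at most 2/22 events has 62% power at a true 10%, and at most 1/18 has 45%. Power first reaches 80% at 31 evaluable subjects, falls to 73–79% at 32–35, and exceeds 80% again from 36. Alternatively, drop the safe/not-safe verdict and report incidences with intervals.
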